9.4.2 ANALYSIS OF THE PRIMARY EFFICACY ENDPOINTS

Primary Objective 1: Compare the extent of **IH** exposure, from randomization through 42 weeks + 6 days PMA (within each gestational week and overall), in infants randomized to extended caffeine treatment to infants assigned to receive placebo.

Analyses for this objective will be performed on the mITT population and compare those randomized to extended caffeine vs. placebo. To be included in **IH** analyses, a subject must have had at least 10 hours of acceptable quality oximetry data recorded within at least one PMA week. A single overall baseline SaO_2

will be determined for each infant, confirmed in our pilot study to be $\geq 95\%$ for the PMA weeks being studied. An **IH** event is defined as SaO_2 decrease $\geq 10\%$ (event threshold) and lasting ≥ 5 sec; the event ends when SaO_2 increases above the event threshold. For sec of SaO_2 below threshold, all sec below the threshold are included. We will compare extended caffeine vs. placebo infants on measures of **IH**, with # of sec $< 90\%$ saturation/day our primary outcome. Our pilot data showed that # of sec $< 90\%$ optimally discriminates between infants on vs. not on extended caffeine, with high correlation between #sec $< 90\%$ saturation/day and multiple other measures to quantify **IH** which will be secondary outcomes, including #**IH** events/day, # sec $< 80\%$ saturation/day, nadir saturation during events, duration of events (Spearman's correlations $r > 0.90$, and AOC during events below 90% and 80% threshold saturation ($r=0.83$).⁹⁰ Preliminary data showed that these outcomes follow a log-normal distribution, and data will be log-transformed for analysis; non-parametric procedures will be considered as an alternative analytic approach if warranted by the distribution of the **IH** outcomes. Exploratory analyses will also compare caffeine vs. placebo on heart rate data. As a check on randomization, preliminary analyses will compare the two study groups on key characteristics including gestational age, birth weight, infant sex, morbidity (e.g., necrotizing enterocolitis, mild BPD), and severity of illness measures; variables found to differ meaningfully between groups will be controlled for in primary analyses through multiple linear regression models. Primary analyses will determine how long extended caffeine provides an advantage over placebo by testing PMA week-specific differences between study groups through multiple regression models controlling for key covariates using Holm's family-wise error adjustment to account for multiple testing across PMA weeks.

Primary Objective 2: Compare changes in a panel of inflammation-related cytokines and chemokines, from enrollment to the target age of 38 weeks + 0 days PMA, in infants randomized to extended caffeine treatment to infants assigned to receive placebo.

Analyses for this objective will be performed on the mITT population and compare those randomized to extended caffeine vs. placebo. To be included in the analyses a subject must have had a baseline/follow-up pair of blood samples for which at least one biomarker was measured on both samples. Analysis will focus on change in inflammatory biomarker levels over the study period. Preliminary analyses will examine the distribution of biomarkers, and data will be transformed (e.g., logged) as appropriate for analysis. Two approaches will be taken for the primary analyses, comparing changes in biomarkers over the study period in extended caffeine vs. placebo infants. First, we will conduct separate analyses of each inflammatory biomarker using linear regression models to compare study groups at study completion, controlling for baseline levels as well as key covariates including morbidities that might be associated with inflammation, using the Benjamini and Hochberg method to account for multiple testing by controlling the false discovery rate. Second, we will examine the structure of the biomarker data using data reduction procedures of factor analyses (identifying latent variables reflected by the set of biomarkers) and latent profile analysis (identifying subgroups of infants with similar patterns of biomarker profiles). Extended caffeine vs. placebo infants would then be compared on the summary measures of inflammation biomarkers resulting from these analyses.

Primary Objective 3: Compare changes in quantitative MRI structural, microstructural and metabolic biomarkers of acute injury, from enrollment to 43-46 weeks PMA, in infants randomized to extended caffeine treatment to infants assigned to receive placebo.

Analyses for this objective will be performed on the mITT population and compare those randomized to extended caffeine vs. placebo. To be included in the analyses a subject must have had a baseline/follow-up pair of MRI studies completed from which at least one MRI endpoint could be measured on both assessments.

Primary neuroimaging outcome measures will include microstructural measures derived from our DTI analyses (FA/MD) and proton MRS. Secondary outcomes will include regional tissue volumes. Individual end-of-study MRI parameters will be compared through analysis of covariance multiple linear regression models controlling for the MRI parameter at baseline along with key covariates including indicators of comorbidities potentially associated with brain development, using the Benjamini and Hochberg method to account for multiple testing by controlling the false discovery rate. .

Secondary Objective 1: Examine the association between salivary caffeine concentrations and **IH** outcomes at the one week post randomization and 40 weeks + 0 days PMA assessments.

Analyses will examine the association between salivary caffeine levels and **IH** outcomes, both at the end of the inpatient stay and at study completion. Caffeine levels at home will also be used to verify protocol adherence. Secondary analyses will also include relationship between individual neonatal morbidities and extent of **IH** in caffeine and placebo groups. Exploratory analyses will model the trends in **IH** parameters over time in the extended caffeine and placebo groups using mixed-effects linear regression models for longitudinal data. Should missing data become a problem, multiple imputation methods will be used to account for potential bias in the complete case analysis.

Secondary Objective 2: Determine whether changes, from baseline to follow-up, in inflammatory or MRI biomarkers are mediated by caffeine-related reduced **IH**.

We will also examine **IH** levels during the study period as a mediator of the extended caffeine effect. Initial analyses will examine associations between **IH** parameters and inflammatory biomarkers, to determine which **IH** measures are most strongly correlated with inflammation at study completion. Linear structural equation mediational models will be used to determine whether any associations between extended caffeine treatment and changes in inflammatory biomarkers can be explained by **IH** parameters during the study period. The relationship between neonatal morbidities, Inflammation, and response to caffeine will also be assessed.

Similarly we will also examine associations between changes in MRI parameters and levels of **IH** during the study period through correlation and linear regression models with the goal of determining **IH** parameters most strongly associated with brain injury. Structural equation mediational models will determine whether any associations between extended caffeine and MRI changes can be explained by the level of **IH** activity during the study.

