1 PROTOCOL SUMMARY

1.1 SYNOPSIS

Title:

Intermittent Hypoxia and Caffeine in Infants Born Preterm (ICAF)

Study Description:

Our proposal will address the critical question: is persisting intermittent hypoxia (**IH**) in preterm infants associated with biochemical, structural, or functional injury, and is this injury attenuated with extended caffeine treatment? We will study the effects of caffeine on **IH** in 220 preterm infants born at ≤ 30 weeks + 6 days gestation. Infants who are currently being treated with routine caffeine, and who meet eligibility criteria, will be enrolled between 32 weeks + 0 days and 36 weeks + 6 days PMA. At enrollment, infants will be started on continuous pulse oximeter recording of O₂ saturation and heart rate. If, based on standard clinical criteria, the last dose of routine caffeine is given on or before the day the infant is 36 weeks + 5 days PMA, then, ideally, on the day following, but no later than the third calendar day following, their last dose of routine caffeine treatment, infants will be randomized (110/group) to extended caffeine treatment or placebo. Randomized infants should begin receiving study drug (i.e. 5 mg/kg/of caffeine base, or equal volume of placebo) on the day of randomization, but no later than the third calendar day following the last dose of routine caffeine. Prior to 36 weeks + 0 days PMA, study drug will be given once daily (i.e. 5mg/kg/day) and beginning at 36 weeks + 0 days PMA, study drug will be given twice daily (i.e. 10 mg/kg/day). The last dose of study drug will be given at 42 weeks + 6 days PMA. **Pulse oximeter**

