4 STUDY DESIGN

4.1 OVERALL DESIGN

HYPOTHESES:

Hypothesis 1: Caffeine will reduce extent of **IH** compared to placebo, and this caffeine effect will persist to 42 weeks PMA.

Hypothesis 2: Extended caffeine treatment will be associated with less acute inflammation at 37-38 weeks compared to placebo, and these effects will be mediated by attenuated **IH**.

Hypothesis 3: Quantitative MRI analyses in the active caffeine group, compared to the placebo group, will be associated with **1)** greater white matter microstructural organization, **2)** improved neuronal metabolism, and **3)** greater regional brain volume, and that these effects will be mediated by attenuated **IH**.

TYPE/DESIGN OF TRIAL:

Randomized, placebo-controlled, double-blinded clinical trial

METHODS TO BE USED TO MINIMIZE BIAS:

All clinical team personnel and all research staff (except research pharmacist) will remain blinded to study group until study completion. Caffeine and equal volume placebo will be prepared by research pharmacist and will be equivalent in color and consistency. The protocol has been designed such that there should be no need to break the code for any individual subject.

NUMBER OF STUDY GROUPS/ARM & STUDY INTERVENTION DURATION:

Infants will be randomized in a 1:1 ratio to 1 of 2 treatment arms, caffeine base (Arm 1) and placebo (Arm 2). Infants from multiple births will be cluster randomized. The duration of the intervention will be from randomization between 32 weeks + 0 days PMA and 36 weeks + 6 days PMA through 42 weeks + 6 days PMA, the age at which extent of **IH** no longer differs from healthy infants born at term.

MULTI-SITE STUDY:

There will be enrollment at multiple hospitals across the U.S.

NAME OF STUDY INTERVENTION:

Caffeine versus placebo

INTERIM ANALYSIS: None planned

STRATIFICATION:

A site-stratified randomly-permuted blocked randomization design will be used to ensure balance at each site. To ensure balance by gestational age at birth, randomization will also be stratified into 2 birth gestational age categories: 1) <28 weeks 2) 28 weeks + 0 days through 30 weeks + 6 days. The randomization scheme will be developed by the DCC using specialized software, and clinical sites will be provided appropriate enrollment logs and randomization procedures from the research pharmacy.

SUB-STUDIES: No ancillary studies planned at this time

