6.3 MEASURES TO MINIMIZE BIAS: RANDOMIZATION AND BLINDING

Randomization:

- Ideally one day following, but up to the third calendar day following the last routine caffeine treatment dose, enrolled infants will be randomized in a 1:1 ratio to 1 of 2 treatment arms, caffeine base or placebo.
- Infants from multiple births will be cluster randomized.
- A site-stratified randomly-permuted blocked randomization design will be used to ensure balance at each site.
- To ensure balance by gestational age at birth, randomization will also be stratified into 2 birth gestational age categories: 1) <28 weeks and 2) 28 weeks + 0 days through 30 weeks + 6 days gestation.
- A randomization scheme will be developed by the DCC using specialized software, and clinical sites will be provided appropriate enrollment logs and blinded randomization procedures.

Blinding:

- Treatment assignments will be blinded until study completion for all study personnel, except for the clinical site research pharmacy dispensing study drug.
- The study pulse oximeter will not have visual displays or alarms for respiration or heart rate activated during the study period ending at 43 weeks + 6 days. The **IH** which is the focus of study typically does not result in overt apnea or bradycardia, and therefore we do not anticipate a need for unblinding based on oximeter results
- Any requests for unblinding will be adjudicated by one of the study Principal Investigators, and can only be authorized by them.
- Two salivary caffeine concentrations are being obtained from all subjects, but the results of the caffeine concentrations will be blinded until all infants have completed the study protocol.
- Potential caffeine side effects, such as mild tachycardia, irritability or feeding difficulties are frequent in both caffeine-treated non-treated infants. If such concerns arise, however, at the discretion of the clinical care team, study drug may be held for the days necessary, and noted in study records, but would generally not be a reason to request unblinding.
- If apnea-related symptoms requiring treatment occur after starting study drug, the clinical care team may institute treatment as needed until cessation of these symptoms, and similarly, this also should not require unblinding.

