9.4 STATISTICAL ANALYSES

9.4.1 GENERAL APPROACH

Statistical significance will be declared at the two-sided $p < 0.05$ level; when appropriate, correction for multiple comparisons will be employed. For analyses of primary and secondary objectives, we will adjust for demographic and clinical differences. When employed, tests for interaction will at the 0.1 alpha level. Results will be presented through measures of effect and 95% confidence intervals. If lost to follow-up exceeds the 10% anticipated under sample size considerations, multiple imputation on the intent-to-treat population will be used for sensitivity analyses that account for missing data. All computations will be performed using the latest available version of SAS®.

Demographic variables and subject characteristics will be summarized descriptively by treatment assignment and overall. Continuous parameters will be summarized using descriptive statistics (N, mean, median, standard deviation, minimum and maximum value). Categorical demographic parameters, such as gender, will be summarized as a percentage of the population.

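### The covariates in the primary weekly IH models are chosen by an undefined imbalance trigger and an unlisted set; the randomisation strata and pre-randomisation IH should be fixed in advance

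*Combined protocol and SAP*

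**What the plan says.** Three statements govern adjustment in the primary IH analysis.

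- Section 9.4.2, Primary Objective 1, begins with a check on randomisation: "preliminary analyses will compare the two study groups on key characteristics including gestational age, birth weight, infant sex, morbidity" and illness severity. It then says that "variables found to differ meaningfully between groups will be controlled for in primary analyses through multiple linear regression models".
- The next sentence defines the primary tests, which compare the arms in each PMA week "through multiple regression models controlling for key covariates", with Holm's correction across weeks. No list of key covariates is given for this objective.
- Section 9.4.1 adds: "For analyses of primary and secondary objectives, we will adjust for demographic and clinical differences".

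On design, section 4.1 states: "A site-stratified randomly-permuted blocked randomization design will be used to ensure balance at each site". Section 6.3 states: "To ensure balance by gestational age at birth, randomization will also be stratified into 2 birth gestational age categories", the categories being below 28 weeks and 28+0 to 30+6 weeks. Section 1.1 states: "At enrollment, infants will be started on continuous pulse oximeter recording". Section 1.2 places baseline data collection between enrolment and randomisation.

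Elsewhere in section 9.4.2, Objective 2 controls for the baseline biomarker level and Objective 3 for the baseline MRI parameter. The single baseline SaO2 mentioned under Objective 1 is a saturation level set beside the IH event definition. It is not a measure of baseline IH burden.

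**The concern.** In a randomised trial the reason to adjust for a covariate is that it predicts the outcome. Whether it happens to differ between arms is a poor guide. A trigger based on imbalance can leave out a strongly prognostic variable because it is balanced, and precision is then lost.

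The trigger is also undefined. The plan names no statistic, cut-off or decision-maker, and the key covariates are open too. The model behind the primary estimate therefore depends on judgements still to be made.

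Three natural covariates are not guaranteed a place: the two stratification factors and the infant's own IH before randomisation. Objective 1, on which the sample size in section 9.2 rests, is the only primary objective without a fixed baseline value in its model. At stake are some efficiency and the pre-specification of the primary analysis.

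**Working it through.** **Inputs from section 9.2.** Effect size d = 0.50; n = 100 per arm; two-sided familywise alpha 0.05 across weeks; outcome assessed from 36 to 42 weeks PMA; stated power 82%.

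**Assumptions.** The first Holm step uses alpha 0.05/k for k weekly tests. The correlation r between log pre-randomisation IH and log on-study IH is not in the documents, so r = 0.2, 0.3 and 0.5 are used. Infants are treated as independent, although "Infants from multiple births will be cluster randomized". Every week is given 100 infants per arm, which later weeks will not reach.

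**Step 1: the plan's own figure.** The noncentrality is d × √(n/2) = 0.5 × √50 = 3.536.

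| k | Normal approximation | t-test |
|---|---|---|
| 6 | 81.5% | 80.7% |
| 7 | 80.1% | 79.2% |

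The stated 82% is reproduced at k = 6. Counting both end weeks gives k = 7, the more cautious case used below.

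**Step 2: fixed baseline adjustment.** Adjustment divides the residual SD by a factor that turns d into d/√(1 − r²). If a share f of infants has no usable baseline, r² becomes r²(1 − f). At alpha 0.05/7, by noncentral t:

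| | r = 0.2 | r = 0.3 | r = 0.5 |
|---|---|---|---|
| Adjusted d, f = 0 | 0.510 | 0.524 | 0.577 |
| Power, f = 0 | 81.2% | 83.7% | 91.2% |
| Power, f = 0.25 | 80.7% | 82.6% | 88.4% |
| Power, f = 0.50 | 80% | 81% | 85% |
| Power, unadjusted | 79.2% | 79.2% | 79.2% |

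**Step 3: what an imbalance trigger recovers.** Trials of 100 per arm were simulated with one prognostic covariate, adjusting only when the trigger fired.

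| Trigger | r = 0.2 | r = 0.3 | r = 0.5 |
|---|---|---|---|
| p < 0.05 to p < 0.20 | 79% | 80–81% | 80–83% |
| Standardised difference > 0.10 | about 80% | about 81% | about 86% |

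Repeat simulations move the second row by up to about one point. Against that row, fixed adjustment with complete baselines gains about 81 − 80 = 1, 84 − 81 = 3 and 91 − 86 = 5 points. The trigger recovers anything only if baseline IH is among the variables screened. The plan's list is open but does not name it.

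**Step 4: how much the undefined cut-off matters.** For an unstratified covariate with no true difference between arms, a p < 0.05 rule admits it in 5% of trials, p < 0.20 in 20%, a standardised difference above 0.25 in 8%, and above 0.10 in 47–48%. The same wording thus covers very different models.

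**Step 5: type I error.** At nominal 5%, with r = 0.3/0.5/0.7, a trigger applied mechanically at p < 0.05 gives 4.7/4.3/3.4%. Omitting a perfectly balanced prognostic stratifier gives 4.0/2.4/0.8%. Both are conservative.

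**Step 6: cost of site terms.** With about 200 infants, 18 extra degrees of freedom cost about 0.1 point. In late weeks fewer infants contribute, because home oximetry depends on the site (section 1.3 footnote 10; section 8.1.1). Assume that half of 8 or 16 sites record at home with 90% retained, and that 10% of infants elsewhere are still inpatients. About 100 infants remain (100 × 0.9 + 100 × 0.1). Site terms then cost 0.8–0.9 point if sites with fewer than 5 infants are pooled, and 2–3 points if not.

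**The case against.** The strongest reply is that key covariates is meant as a set entered unconditionally. Objectives 2 and 3 use the same phrase that way, and the preceding sentence under Objective 1 calls gestational age a key characteristic. On that reading gestational age is in every weekly model. This stands as a fair reading. A reader might infer that gestational age is confined to the imbalance check, and the text does not establish that. It leaves the matter open and still names neither site nor pre-randomisation IH.

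A reader might also infer that stratified randomisation would keep gestational age from ever meeting the trigger. That does not follow: the plan screens gestational age, and blocking on two categories does not balance it within each category.

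The size of the gain can be challenged too. The correlation is unknown. It may be low, because baseline is recorded on or just after routine caffeine, possibly on nasal CPAP (section 5.1, criterion 5), and at varying ages. Some baselines will be short or absent, since criterion 2 admits infants up to the third calendar day after the last routine dose. With half missing and r of 0.2 to 0.3, the gain is only 1 to 2 points over no adjustment. All the gains shown come from baseline IH; none has been quantified for site or gestational-age stratum. These limits stand. They reduce the size of the benefit and do not justify the trigger.

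**Conclusion.** The point holds as one of pre-specification and efficiency. The plan states a weaker rule where a better one is available from data it already collects, and which its other two primary objectives already follow for the baseline value. Confidence in the textual gap is high.

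The realistic gain is a few points of first-step power. It rests on the assumed correlations, alpha 0.05/7 and 100 infants per arm in each week. The 91% at r = 0.5 is the favourable end of the range.

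Two stronger readings are not supported. The 79% should not be taken as a correction of the stated 82%: it comes from counting seven weeks and using a t-test, and the plan's figure reproduces with six. Nor do the documents show an inflated type I error. An analyst free to pick the better of the adjusted and unadjusted results would reach 6.5/7.4/7.7% at r = 0.3/0.5/0.7 with one covariate, but nothing suggests such a choice is intended, and a trigger applied by rule is conservative.

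**What to change.** Before unblinding, replace the trigger with one named covariate set used in every weekly IH model:

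- birth gestational-age stratum;
- site, with small sites pooled by a single rule that is set before unblinding, used in all weeks and allows for sites without home oximetry;
- log-transformed seconds below 90% per 24 hours from pre-randomisation recording, with a small stated constant added for zeros.

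Count a baseline only if it has at least 10 acceptable pre-randomisation hours, which borrows the plan's minimum for outcome data. Otherwise enter the overall mean and a missing-baseline indicator. State which other listed characteristics, if any, enter every model. Keep the comparison of baseline characteristics descriptive, and move adjustment for observed imbalance to a sensitivity analysis.

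The cost is SAP wording and minor programming, with no new data collection. Some baselines will be short or missing, in a share the documents do not give, and site terms will cost a little power in late weeks.

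### Siblings are randomised together within site and gestational-age strata, but no primary analysis accounts for sibling sets or prespecifies the strata, and the 82% power mentions no design effect.

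*Combined protocol and SAP*

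**What the plan says.** **Design (sections 4.1 and 6.3).** "Infants from multiple births will be cluster randomized", so for multiples the randomised unit is the sibling set. Also: "A site-stratified randomly-permuted blocked randomization design will be used to ensure balance at each site", and "randomization will also be stratified into 2 birth gestational age categories" (below 28 weeks, and 28 weeks + 0 days through 30 weeks + 6 days).

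**Analysis (section 9.4).**
- General approach: "For analyses of primary and secondary objectives, we will adjust for demographic and clinical differences". No variables are listed there.
- Objective 1: the primary analysis works by "testing PMA week-specific differences between study groups through multiple regression models controlling for key covariates", with Holm's "family-wise error adjustment to account for multiple testing across PMA weeks". Gestational age is among the characteristics compared as a check on randomisation, and "variables found to differ meaningfully between groups will be controlled for in primary analyses through multiple linear regression models". If the distribution calls for it, "non-parametric procedures will be considered as an alternative analytic approach".
- Objective 2: linear regression on each biomarker, adjusted for baseline and an open list of covariates that includes morbidities. A second primary approach compares the arms on factor or latent-profile summaries.
- Objective 3: analysis of covariance on each MRI parameter, adjusted for baseline and an open list that includes comorbidities.

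Section 9 never mentions siblings, a random family effect, GEE or robust variance, and never names site as a covariate. Its only mixed model is exploratory and concerns trends over time.

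**Power (section 9.2).** 100 infants per group give 82% power for an effect size of 0.50 at an overall two-sided 0.05 level, corrected across weeks 36 to 42. Sibling share, intra-sibling correlation and design effect are not mentioned.

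**The concern.** The design and the analysis disagree about the independent unit. Two features are left out, and they act in opposite directions.

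- **Sibling sets.** Siblings share an arm and probably resemble each other in outcome. If they are counted as independent, standard errors are too small when the residual sibling correlation is positive.
- **Strata.** Stratified blocking removes between-stratum variation from the treatment contrast. If the strata predict outcome and are left out of the model, that variation stays in the residual and standard errors are too large.

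Which effect dominates depends on covariate lists that the plan leaves open. For Objective 1, gestational age enters only if an imbalance is seen. The errors pass into every 95% confidence interval and into the p-values used by Holm (Objective 1) and Benjamini-Hochberg (Objectives 2 and 3). Neither procedure repairs p-values that are wrong on entry.

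**Working it through.** **1. The plan's own figure.** Inputs from section 9.2: n = 100 per group, d = 0.50, overall two-sided 0.05. The number of weekly tests is not stated; it is 7 if each of weeks 36-42 is tested. With independent infants and a normal approximation at 0.05/k, power is 80.1% for k = 7 and 81.5% for k = 6. The noncentral t gives 79.2% for k = 7. The stated 82% is within two points of the normal-approximation figures with a design effect of 1, so nothing in it suggests an allowance for clustering.

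**2. Design effect.** DE = 1 + ((Σm²/Σm) − 1) × ICC, where m is sibling-set size. If a share f of infants is in twin pairs and the rest are single, Σm²/Σm = 2f + (1 − f) = 1 + f, so DE = 1 + f × ICC. The documents give neither f nor ICC; the values below are assumptions.

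**3. Size and power, strata in the model.** True size of a test that ignores siblings is 2(1 − Φ(z/√DE)). For DE = 1.06: 1.960/√1.06 = 1.904, which gives 0.057. The power columns are for an analysis that does allow for siblings, using n = 100/DE per arm, 7 tests and d = 0.5. One-week power is the noncentral t at 0.05/7. All-weeks power is simulated Holm per-week power, over between-week correlations of 0.3-0.7 (assumed) and both t-test and normal-approximation runs.

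| f, ICC | DE | Size at nominal 0.05 | Size at nominal 0.05/7 = 0.0071 | Power, effect in one week only | Power per week, effect in all weeks |
|---|---|---|---|---|---|
| none | 1.00 | 0.050 | 0.0071 | 0.792 | 0.869-0.900 |
| 0.1, 0.1 | 1.01 | 0.051 | 0.0074 | 0.787 | not run |
| 0.2, 0.3 | 1.06 | 0.057 | 0.0090 | 0.761 | 0.846-0.878 |
| 0.3, 0.5 | 1.15 | 0.068 | 0.0121 | 0.716 | 0.807-0.840 |
| 0.4, 0.7 | 1.28 | 0.083 | 0.0174 | 0.655 | 0.751-0.784 |

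With the pilot effects of section 9.2 at weeks 37 and 38 (0.87, 0.73) and 0.5 in the other weeks, DE 1.28 leaves at least 97% power at weeks 37-38 and 79-80% elsewhere.

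**4. Size under four models.** Families were simulated in permuted blocks of 4 within site × gestational-age category, with total variance 1 and strata entered as main effects. There were 8,000 runs per row (Monte Carlo SE 0.0024). Block size and site numbers (12 for 200 infants, 6 for 110) are assumed; 110 is the MRI target of 55 per arm in section 8.1.3. Entries are the true size of a nominal 0.05 test.

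| Infants | Twin share / family variance / stratum variance | Neither | Strata only | Family only | Both |
|---|---|---|---|---|---|
| 200 | 0.2 / 0.3 / 0.1 | 0.047 | 0.058 | 0.040 | 0.050 |
| 200 | 0.2 / 0.3 / 0 | 0.053 | 0.051 | 0.047 | 0.045 |
| 200 | 0.3 / 0.5 / 0 | 0.070 | 0.069 | 0.050 | 0.049 |
| 200 | 0.3 / 0.35 / 0.15 | 0.051 | 0.066 | 0.038 | 0.052 |
| 200 | 0.4 / 0.5 / 0.2 | 0.062 | 0.082 | 0.029 | 0.050 |
| 200 | 0.4 / 0.7 / 0 | 0.081 | 0.081 | 0.049 | 0.048 |
| 110 | 0.2 / 0.3 / 0.1 | 0.050 | 0.062 | 0.043 | 0.053 |
| 110 | 0.3 / 0.35 / 0.15 | 0.051 | 0.065 | 0.037 | 0.052 |
| 110 | 0.3 / 0.5 / 0 | 0.064 | 0.064 | 0.050 | 0.050 |
| 110 | 0.4 / 0.5 / 0.2 | 0.057 | 0.075 | 0.031 | 0.048 |
| 110 | 0.4 / 0.7 / 0 | 0.087 | 0.088 | 0.051 | 0.051 |

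A further case with strongly predictive strata (0.3 / 0.25 / 0.25, 10,000 runs) gave 0.038 with neither term, so the error can also be conservative. Only the model with both terms stays close to nominal throughout (0.045-0.053). Strata plus an ordinary cluster-robust variance (CR1) gave 0.046-0.058, which is why a small-sample correction is needed.

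**The case against.** The omissions are not in dispute; their importance is.

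- **The two gaps partly cancel.** With neither term, the 20%-twins cases give 0.047, 0.053 and 0.050, which is nominal within simulation error. Values above 0.062 occur only where the strata predict nothing, and that is the less natural assumption for factors chosen for stratification. This stands. The sizes in step 3 apply only once the strata are in the model.
- **The power losses belong to the corrected analysis.** The uncorrected test at DE 1.28 would reject about 77% of the time (normal approximation, 7 tests), with inflated size. Of the gap between 82% and 76% in the middle case, about 3 points are already there at DE 1. Any precision gained from predictive strata is not credited. This also stands.
- **Siblings may not be the main threat to power.** Discharge is commonly at 34-40 weeks (section 1.1) and home oximetry runs only at some sites (section 8.1.1), so 100 recordings per arm in every week is doubtful. This is fair, and the power columns are best read as relative losses.

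None of this closes the gap. Cancellation that depends on unknown quantities is no safeguard, and half a fix can do harm: adding only the strata moves size from 0.047 to 0.058, or from 0.062 to 0.082, while adding only a family term can bring it down to 0.029. The open covariate lists might turn out to include site or gestational age, but no covariate corrects the variance for siblings.

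**Conclusion.** The concern holds. Followed as written, the plan gives standard errors that do not match the randomisation, and it does not settle the direction of the error. Under the assumed ranges, true size at a nominal 0.05 is 0.051-0.083 with strata in the model and about 0.038-0.087 with neither term. The upper ends are extreme cases (40% of infants in twin pairs, high sibling correlation), and the middle case is mild.

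The 82% is not arithmetically wrong. If d = 0.5 holds in every week it roughly survives a design effect of 1.15. If the effect is confined to one week, power falls from 79% to 76%, 72% and 65% at design effects of 1.06, 1.15 and 1.28.

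The omission is certain from the text. Its size rests on assumed multiples share, sibling correlation, between-week correlation, site numbers and block size. It should be fixed because the remedy is nearly free and the choice should not be made after the data are seen.

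**What to change.** **Section 9.4.2**
- Fit all primary regressions, the Objective 2 comparisons of factor and profile summaries, and secondary regressions on the same outcomes with birth family as the cluster. Use either a random family intercept, or GEE or cluster-robust variance with a small-sample correction.
- Prespecify site and gestational-age category as covariates whatever the observed balance. In the MRI subset enter them as main effects, pooling small sites if needed.
- Make any non-parametric alternative respect families, for example by permuting whole families within strata.

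**Section 9.2**
- State the number of weekly tests, and restate power under Holm with the design effect of step 2, over a declared range of multiples share and residual sibling correlation.

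**Cost.** A few sentences, one model term and the strata covariates in the SAS code. Stated power will be slightly lower and a few degrees of freedom are lost, mostly felt in the MRI subset, whose number of sites is not given. No new data are needed and enrolment does not change.
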